### **Secondary objectives**

- To compare incidence of low output syndrome after off-pump CABG, on-pump CABG and pump-assisted CABG (with cardiopulmonary bypass without aortic cross-clamping)
- To compare length of stay in intensive care unit after off-pump CABG, on-pump CABG and pump-assisted CABG (with cardiopulmonary bypass without aortic cross-clamping)
- To compare length of stay in hospital care unit after off-pump CABG, on-pump CABG and pump-assisted CABG (with cardiopulmonary bypass without aortic cross-clamping)

# Assessment of Myocardial Ischemic-Reperfusion Injury During Off- and On- Pump CABG

(ClinicalTrials.gov Identifier: NCT03050489). Corresponding author: [name]

[[contact]](mailto:[contact]) [contact]

Date of the document 06 December 2016

- To compare inotrope and vasopressor agents demand after off-pump CABG, on-pump CABG and pump-assisted CABG (with cardiopulmonary bypass without aortic cross-clamping)
- To compare duration of pulmonary ventilation after off-pump CABG, on-pump CABG and pump-assisted CABG (with cardiopulmonary bypass without aortic cross-clamping)
- To compare end systolic volume, end diastolic volume, ejection fraction after off-pump CABG, on-pump CABG and pump-assisted CABG (with cardiopulmonary bypass without aortic cross-clamping)
- To investigate whether MPO level could predict outcomes after CABG
- To compare incidence of reoperation after off-pump CABG, on-pump CABG and pump-assisted CABG (with cardiopulmonary bypass without aortic cross-clamping)
- To compare incidence of renal dysfunction after off-pump CABG, on-pump CABG and pump-assisted CABG (with cardiopulmonary bypass without aortic cross-clamping)
- To compare incidence of atrial fibrillation after off-pump CABG, on-pump CABG and pump-assisted CABG (with cardiopulmonary bypass without aortic cross-clamping)
- To compare incidence of death during 30 days after off-pump CABG, on-pump CABG and pump-assisted CABG (with cardiopulmonary bypass without aortic cross-clamping)
- To compare incidence of stroke during 30-days after off-pump CABG, on-pump CABG and pump-assisted CABG (with cardiopulmonary bypass without aortic cross-clamping)

## Study population

- Patients with multivessel coronary artery lesions with indications for elective CABG

## Inclusion criteria

- Multivessel coronary artery disease with indications for CABG
- Single CABG procedure

Assessment of Myocardial Ischemic-Reperfusion Injury During Off- and On- Pump CABG (ClinicalTrials.gov Identifier: NCT03050489). Corresponding author: [name] [[contact]](mailto:[contact]) [contact]

Date of the document 06 December 2016

#### **Exclusion criteria**

- Valve disease
- Acute coronary syndrome or urgent CABG

#### **Study timepoints**

- During 30 days after CABG

#### **Myeloperoxidase Test**

Biomaterial production protocol:

1st test before surgery. Blood is obtained from a central venous catheter in a volume of 4 ml into a violet tube. Within 7 minutes, centrifugation at 3000 rpm at 4 ° C is carried out. The plasma is then collected into an eppendorf-type tube of 1 ml and frozen at -40 or below.

The 2nd test immediately after performing coronary artery suture. Blood is obtained from a central venous catheter in a volume of 4 ml into a violet tube. Within 7 minutes, centrifugation at 3000 rpm at 4 ° C is carried out. The plasma is then collected into an eppendorf-type tube of 1 ml and frozen at -40 or below. Samples, they are delivered to the laboratory of biochemical genetics of the Institute of Experimental Medicine, where molecular and biological studies are performed. The receipt of the material was approved by the ethical committee of the First State Medical University after I.P.Pavlov, protocol 03 / 17-11.

Earlier we worked out methods for isolating homogeneous preparations of myeloperoxidase (MPO) [11]. The preparations of MPO ( $M \sim 145$  kDa,  $RZ \sim 0.85$ ) obtained with the help of original approaches do not contain impurities of leukocyte proteinases and differ in the specific activity that exceeds commercially available analogs. For the quantitative determination of MPO, previously used solid-phase enzyme-linked immunosorbent assays will be used, which are characterized by high sensitivity and specificity due to the independent production of monovalent antibodies against the proteins.

The activity of MPO in the samples is estimated from the fluorescence of resorufin, which is formed by oxidation of 10-acetyl-3,7-dihydroxyphenoxazine with brominating MPO, which binds when the samples are incubated in plates with adsorbed on the surface of the wells with affinity antibodies against MPO obtained from rats [4]. Antibodies (5  $\mu$ g / ml) dissolved in 40 mM Na2CO3, 80 mM NaHCO3, pH 9.4, are adsorbed in 96-well polystyrene plates overnight at 4 ° C. After 3 washes of PBS containing 0.05% Tween 20, the purified MPO was placed in the wells at 0 concentrations; 0.625; 1.25; 2.5; 5; 10; 20; 40 ng / ml and samples diluted 10 to 80 times with PBS containing 0.05% Tween 20. After 60 min incubation in a thermoshaker at 37 ° C and 270 rpm, the wells of the plate are washed 3 times with PBS containing 0.05% Tween 20. A solution containing 1  $\mu$ M 10-acetyl-3,7-dihydroxyphenoxazine, 10  $\mu$ M H2O2, 20 mM NaBr, 200 mM (NH4)2SO4, 24 mM sodium citrate buffer, pH 6.0 is placed in the wells. After 30 minutes of incubation in a thermoshaker at 37 ° C and 270 rpm, the fluorescence of the resorufin at 580-620 nm (535-555 nm excitation) was measured using a flatbed monochromator fluorimeter-luminometer

Assessment of Myocardial Ischemic-Reperfusion Injury During Off- and On- Pump CABG (ClinicalTrials.gov Identifier: NCT03050489). Corresponding author: [name] [[contact]](mailto:[contact]) [contact]

Date of the document 06 December 2016

spectrophotometer ("CLARIOstar", BMG LABTECH, Germany). The calibration plot of the fluorescence intensity I from [MPO] is processed in the MS Excel 2002 program as the binomial function  $I = a [MPO]^2 + b [MPO] + c$  (the coefficient of determinism R2 normalized from 0 to 1). The activity of MPO in the samples was calculated taking into account the dilution of the sample and expressed as ng / ml of purified MPO.

In order to optimize the methods for determining the activity of these enzyme, the conditions of sorption from plasma of blood on solid-phase immobilized antibodies, dissociation conditions of inhibitors will be studied when their activity is detected. The results obtained will be compared with the results of the determination using traditional methods of enzyme immunoassay. As a result, optimal protocols will be obtained for rapid tests to detect the activity of myeloperoxidase in blood plasma after immunosorption.

### **Safety Analysis**

Adverse events (AEs)/serious AEs.

### **Study Duration**

The date of the first subject inclusion – 15 September 2015.

Estimated date of the last subject inclusion – May 2019 .

Expected date of database closing – October 2019.

Study report ready –2020

### **Definitions**

#### **Ischemic-Reperfusion Injury**

Myocardial ischemic – reperfusion injury defined as troponin I elevation after CABG higher than upper reference limit (URL) in patients who does not met current criteria for myocardial infarction 5 type diagnosis.

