Title	Assessment of Myocardial Ischemic-Reperfusion Injury During Off- and On- Pump CABG (AMIRI-CABG) ClinicalTrials.gov Identifier: NCT03050489	
Authors *	[name]	
Trial design	Prospective non-randomized single center	
Methods		
Participants	Eligibility criteria: multivessel coronary artery disease with indications for elective coronary artery bypass grafting	
Interventions	Group 1: off-pump CABG Group 2: on-pump CABG Group 3: pump-assisted CABG (on-pump CABG without aortic cross-clamping)	
Objective	To compare level of MPO between three groups of intervention	
Primary objective	To compare ischemic-reperfusion injury between three groups of intervention	

Assessment of Myocardial Ischemic-Reperfusion Injury During Off- and On- Pump CABG  
 (ClinicalTrials.gov Identifier: NCT03050489). Corresponding author: [name]  
[[contact]](mailto:[contact]) [contact]

Date of the document 06 December 2016

Secondary objective	To assess ability of MPO to predict worse outcome (death) To assess relation between MPO and TnI	
Outcome	MPO level after CABG, death after CABG	
Randomization	Non-randomized allocation. Heart Team decision.	
Blinding (masking)	None	
Results		
Numbers randomized	Number of participants screened n=500  Allocated (non-randomized): off-pump CABG (n=181), on-pump CABG (n=128), pump-assisted CABG (n=27)	
Recruitment	Complete	
Numbers analyzed	Off-pump CABG: 181 On-pump CABG: 128 Pump-assisted CABG: 27	
Outcome	Could MPO predict death during 30 days after CABG	
Harms	Important adverse events or side effects	
Conclusions	CPB activates leucocytes that cause myocardial damage  Preoperative MPO level could evaluated as a predictor of myocardial damage and worse outcome after CABG	
Trial registration	ClinicalTrials.gov Identifier: NCT03050489	
Funding	Assessment of regenerative ability after cardiac surgery	

*Table 2 Statistical analysis synopsis*

Assessment of Myocardial Ischemic-Reperfusion Injury During Off- and On- Pump CABG ClinicalTrials.gov Identifier: NCT03050489	
Hypothesis	Ischemic – reperfusion injury are comparable between groups
Primary objective	To compare ischemic-reperfusion injury during off-pump, on-pump and pump – assisted CABG
Secondary objective	To assess ability of myeloperoxidase to predict worse outcome after CABG

Assessment of Myocardial Ischemic-Reperfusion Injury During Off- and On- Pump CABG  
 (ClinicalTrials.gov Identifier: NCT03050489). Corresponding author: [name]  

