[[contact]](mailto:[contact]) [contact]

Date of the document 06 December 2016

Type of trial	Prospective non-randomised single-centre
Type of research	Exploratory
Timeline	2015-2019
Groups	Off-pump  On – pump  Pump-assisted (on-pump without aortic cross-clamping)
Sample size estimation	> 300 patients
Planned sample size	Average: 300  Off-pump: 100  On-pump: 100  Pump-assisted: 100
Actual sample size	Average: 336  Off-pump: 181 (conversion 6)  On-pump: 128  Pump-assisted: 27
Baseline characteristics comparing	Testing for type of distribution of baseline characteristics:  ANOVA for normal distribution  Kruskal-Wallis test with multiple groups comparison adjustment for non-normal distribution  Chi-squared test or exact Fisher's test for nominal data
Statistics hypothesis testing	ANOVA/ANCOVA for MPO level, troponin I level
Missing Data Handling	Drop observations with missing data
Evaluating of reason of missingness	Hypothesis: Missing data depend on severity of complications  Hypothesis testing with logistic regression model: Missingness = complications

Assessment of Myocardial Ischemic-Reperfusion Injury During Off- and On- Pump CABG  
(ClinicalTrials.gov Identifier: NCT03050489). Corresponding author: [name]  
[[contact]](mailto:[contact]) [contact]

Date of the document 06 December 2016

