### **Study objectives**

- To compare ischemic-reperfusion injury after off-pump, on-pump and pump-assisted - CABG

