### **Primary objective**

- To compare MPO level before and just after performing coronary anastomosis during off-pump CABG, on-pump CABG and pump-assisted CABG (with cardiopulmonary bypass without aortic cross-clamping)
- To compare TnI level between groups

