#### **Myocardial Infarction 5 Type**

Myocardial Infarction 5 type defined as a troponin I elevation higher than 10 time 99th percentile URL with new Q-wave onset (ECG) or new regional wall motion abnormality (echocardiography) or graft/new coronary artery occlusion (angiography).

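### Comparing ischemic-reperfusion injury is the stated objective and the injury is defined, but no troponin I analysis applies the definition

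*Combined protocol and SAP*

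**What the plan says.** **Objective.** The primary objective in Table 1 is "To compare ischemic-reperfusion injury between three groups of intervention". The Study objectives section says the same: "To compare ischemic-reperfusion injury after off-pump, on-pump and pump-assisted - CABG". The synopsis (Table 2) repeats it and makes comparable injury between groups the hypothesis.

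**Definition.** Under Definitions, the injury is a post-CABG TnI above the URL "in patients who does not met current criteria for myocardial infarction 5 type diagnosis". The type 5 infarction definition requires "troponin I elevation higher than 10 time 99" (the 99th-percentile URL is meant), together with a new ECG Q wave, a new wall-motion abnormality on echo, or an occluded graft or coronary artery on angiography.

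**A different wording.** The section headed Primary objective lists MPO before and after the anastomoses and "To compare TnI level between groups". Study Design names postoperative MPO as the primary endpoint.

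**Analysis.** The synopsis plans "ANOVA/ANCOVA for MPO level, troponin I level" and states one exclusion rule, for missing data. Four day-1 TnI models (pooled, on-pump, off-pump, pump-assisted) are headed as ischemic-reperfusion injury analyses. So is an MPO model, although MPO is not part of the definition. TnI by day is tabulated for all patients (Table 30), for those without low cardiac output syndrome (a second table numbered 30) and for those with it (Table 31).

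**The concern.** The definition has two parts: a threshold (TnI above the URL) and an exclusion (no type 5 infarction). An analysis of the injury so defined needs the URL, a type 5 classification for each patient, and a count or comparison of patients who meet both parts. A comparison of TnI level in everyone measured is a different quantity. It includes patients below the URL and any patients with type 5 infarction, whom the definition keeps apart.

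If the level comparison is reported under the injury heading, readers will take a difference in TnI as a difference in reperfusion injury. Part of it could come from infarction or graft occlusion, and the document gives no means of telling how much.

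**Working it through.** **1. Definition against analysis**

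| Needed by the definition | Found in the document |
|---|---|
| URL value | Not stated; nor is it said whether the injury URL is the 99th percentile used for type 5 infarction |
| Type 5 infarction by group | Not tabulated |
| Injury as defined, by group | Not tabulated |
| TnI analysis without type 5 infarction | None |
| TnI analysis restricted to values above the URL, or a binary injury outcome | None; the models use log TnI and the tables use TnI level |

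**2. Could the TnI tables contain an unstated exclusion?** Inputs: group sizes, day-1 missing counts (Nmiss) and day-1 means from both tables numbered 30 and from Table 31.

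- Analysed on day 1 in the all-patient table: 181−17 = 164, 128−10 = 118, 27−1 = 26, in total 308 of 336. This is everyone with a measurement.
- The low-output strata add back to the full groups: 166+15 = 181, 113+15 = 128, 26+1 = 27.
- Their day-1 missing counts add back too: 14+3 = 17, 8+2 = 10, 1+0 = 1.
- Pooled day-1 means, using n minus Nmiss as weights:
  - off-pump (152×1.1 + 12×20.0)/164 = 2.48, table 2.5
  - on-pump (105×4.1 + 13×21.0)/118 = 5.96, table 6.0
  - pump-assisted (25×4.1 + 17.6)/26 = 4.62, table 4.7 (within rounding of the inputs)

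So no measured patient was removed from these tables for type 5 infarction.

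**3. Could the models contain one?** Implied n = SSE/MSE + model df + 1, with SSE = SS(1−η²)/η² and MSE = (SS/df)/F, from Tables 12, 15, 18 and 21. For the pooled model, SSE = 249.3×0.56/0.44 = 317.3 and MSE = (249.3/14)/10.4 = 1.712, so n = 185.3 + 15 ≈ 200. The complete-case limits come from the missing counts for preoperative MPO, postoperative MPO and day-1 TnI. The upper limit subtracts the largest count and the lower limit subtracts their sum.

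| Model | Implied n | Complete-case limits |
|---|---|---|
| Pooled | about 200 (196–205) | 177–263 (sums of the rows below) |
| On-pump | about 74 (72–76 if η² is 0.40; 61–90 if it is 0.4 to one decimal) | 71–102 |
| Off-pump | about 123 (118–129) | 102–147 |
| Pump-assisted | about 9 | 4–14 |

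Missing data alone can explain these sizes. They give no sign of a type 5 exclusion, and none is stated.

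**4. Why the missing URL matters.** Day-1 quartile ranges in the all-patient Table 30 are 0.2–1.0 (off-pump), 1.8–6.3 (on-pump) and 0.7–6.8 (pump-assisted). Taking those figures as assumed limits, a URL below 0.2 would put about three quarters or more of every group above it. A URL of 1.0 would put about one quarter of off-pump but more than three quarters of on-pump patients above it. The injury comparison therefore cannot be recovered from the tables, even before type 5 infarction is considered.

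**5. What the low-output split shows.** Day-1 figures, all patients against those without low output:

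| | All | Without low output |
|---|---|---|
| Mean, off-pump / on-pump | 2.5 / 6.0 | 1.1 / 4.1 |
| On/off ratio of means | 6.0/2.5 = 2.4 | 4.1/1.1 = 3.7 |
| Median, off-pump / on-pump | 0.4 / 3.1 | 0.4 / 2.5 |
| On/off ratio of medians | 3.1/0.4 ≈ 7.8 | 2.5/0.4 ≈ 6.3 |
| P value (three groups) | <.0001 | <.0001 |

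The ratio of means rises while the ratio of medians does not. The TnI tables name no test. I take it to be Kruskal-Wallis, as the Secondary Endpoint Analysis section plans for non-normal variables.

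**The case against.** The best defence is that the section headed Primary objective asks for a comparison of TnI level, and that comparison is reported. The primary endpoint is postoperative MPO, which this point does not touch. TnI level also keeps information that a threshold discards. Removing type 5 infarction conditions on a post-operative event that technique may influence, in a comparison that is already non-randomised. All of this stands. It justifies keeping the all-patient analysis. It does not remove the conflict, because Table 1, Table 2 and Study objectives name the injury, and the model headings present unrestricted TnI as that injury.

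Three stronger readings are tempting, and the documents do not support them.

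- *Every TnI analysis includes all patients.* Two tables are low-output subsets, three models cover one procedure each, and all the models drop patients with missing data. What is true is that none excludes type 5 infarction or applies the URL.
- *A few infarctions or graft failures drive the TnI difference.* Low output syndrome is not a type 5 criterion. The 13 graft thromboses (6/6/1) are counted over 30 days and not linked to TnI. The highest value, 98.0, is known only to belong to a low-output patient. The shift from 2.4 to 3.7 is in means of very skewed data (off-pump 2.5±8.9), whereas the plan uses ranks and logs, and the medians barely move.
- *The primary objective is not analysed at all.* As worded in the section of that name, it is.

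**Conclusion.** The point holds as a mismatch between objective, definition and analysis. Ischemic-reperfusion injury as the document defines it is never derived, counted or compared, and the sections stating the objective contradict one another.

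The size of any effect on the TnI comparison is unknown, because neither the URL nor the number of type 5 infarctions is given. The low-output split cannot supply it. It shows only that the day-1 difference survives removal of that subgroup at p<.0001, so a reader should not infer that the TnI difference is an artefact of infarction. The P value is read as a rank test, which is an assumption.

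This should be corrected before any result is described as ischemic-reperfusion injury. It does not affect the MPO endpoint.

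**What to change.** 1. State the URL and assay unit, and say whether the injury threshold is the same 99th-percentile limit used for type 5 infarction.
2. Classify type 5 infarction by the document's own criteria from data already recorded. Report by group the numbers with type 5 infarction, with injury as defined, with neither, and unclassifiable, and give the rule for calling a patient unclassifiable.
3. Compare the incidence of injury as defined between groups.
4. Repeat the all-patient Table 30 and the log-TnI ANCOVA without type 5 patients as an added analysis. Print the all-patient result beside it, and note that the exclusion conditions on a post-operative event.
5. If classification is not feasible, reword the objective (Tables 1 and 2, Study objectives), the definition and the section headings as a comparison of TnI and MPO levels in all patients, and do not call the result ischemic-reperfusion injury.

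**Cost.** Chart classification, a rerun, and slightly fewer patients in the added analysis; no new enrolment. Some patients will stay unclassifiable. TnI is missing in 17+10+1 = 28 of 336 on day 1 and in 104+39+9 = 152 of 336 (45%) on day 2. Postoperative echo volumes are missing in 11–17% by group, and no ECG or angiography schedule is shown. Route 5 costs only an edit, but gives up the claim about injury.

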#### **Myocardial Infarction 5 Type**

Myocardial Infarction 5 type defined as a troponin I elevation higher than 10 time 99th percentile URL with new Q-wave onset (ECG) or new regional wall motion abnormality (echocardiography) or graft/new coronary artery occlusion (angiography).

### **Adverse Events**

An Adverse Event (AE) is defined as any new untoward medical occurrence or worsening of a preexisting medical condition in a clinical investigation of procedure and not necessarily have a causal relationship with this treatment. An AE can therefore be any unfavorable and unintended sign (such as an abnormal laboratory finding), symptom, or disease temporally associated with the use of investigational procedure, whether or not considered related to the investigational procedure.

The causal relationship to study drug is determined by a physician and should be used to assess all adverse events (AE). The causal relationship can be one of the following:

Related: There is a reasonable causal relationship between study procedure and the AE.

The term "reasonable causal relationship" means there is evidence to suggest a causal relationship.

Adverse events can be spontaneously reported or elicited during open-ended questioning, examination, or evaluation of a subject. (In order to prevent reporting bias, subjects should not be questioned regarding the specific occurrence of one or more AEs.)

### **Serious Adverse Events**

A Serious Adverse Event (SAE):

results in death is life-threatening (defined as an event in which the subject was at risk of death at the time of the event; it does not refer to an event which hypothetically might have caused death if it were more severe) requires inpatient hospitalization or causes prolongation of existing hospitalization (see NOTE below) results in persistent or significant disability/incapacity is a congenital anomaly/birth defect is an important medical event (defined as a medical event(s) that may not be immediately life-threatening or result in death or hospitalization but, based upon appropriate medical and scientific judgment, may jeopardize the subject or may require intervention [eg, medical, surgical] to prevent one of the other serious outcomes listed in the definition above.) Examples of such events include, but are not limited to, intensive treatment in an emergency room or at home for allergic bronchospasm; blood dyscrasias or convulsions that do not result in hospitalization.)

### **Nonserious Adverse Events**

A nonserious adverse event is an AE not classified as serious.

### **Laboratory Test Abnormalities**

All laboratory test results captured as part of the study should be recorded following institutional procedures. Test results that constitute SAEs should be documented and reported as such.

Collection and reporting

